3.2.2.2 Sensitivity Analysis

The Primary analysis method will be repeated in the PP population.

3.2.2.3 Subgroup Analysis

The primary analyses of the key secondary endpoints will be repeated for subgroups defined by the following baseline variables:

- Age group (12-18 yrs, ≥ 18 yrs)
- Sex (male, female)
- Weight group (<40 , ≥ 40 kg)

Subgroups could be collapsed if the number of participants in some subgroups is too small.

3.2.3 Other Secondary Efficacy Endpoints

All the other secondary endpoints analysis will be done in the ITT population. The secondary endpoints will be analyzed descriptively. No formal statistical comparisons are planned for these endpoints.

3.2.3.1 Proportion of Participants With Any Escalation of Treatment in the First 24 Hours Following IP Initiation

Proportion of participants with any escalation of treatment in the first 24 hours following IP initiation, i.e. any medication other than IP administered for the acute treatment of SE in the first 24 hours following IP initiation will be summarized by count and percentage of participants by treatment group. The 95% CIs will be also calculated using Clopper-Pearson method.

3.2.3.2 Time to Treatment Escalation Following IP Initiation

For time to treatment escalation following IP initiation (any medication used for acute treatment of SE), the quartiles (1st [25% percentile], 2nd [median], 3rd [75% percentile]) and the associated 95% CI will be provided based on the Kaplan-Meier estimate of the survival curves. For participants without treatment escalation, the time to treatment escalation will be censored at IP completion, or discontinuation from the study or death, whichever occurs earlier.

3.2.3.3 Time to Initiation of Anesthesia for SE Treatment Through the Final Study Follow-up Visit/Contact

For time to initiation of anesthesia for SE treatment through the final study follow-up visit/contact, the quartiles (1st [25% percentile], 2nd [median], 3rd [75% percentile]) and the associated 95% CI will be provided based on the Kaplan-Meier estimate of the survival curves. For participants without initiation of anesthesia for SE treatment, the time to initiation of anesthesia will be censored at IP completion, discontinuation from the study or death, whichever occurs first.

3.2.3.4 Proportion of Participants Who Develop Super Refractory SE (SRSE) Through the Final Study Follow-up Visit/Contact

Count and percentage of participants who develop SRSE through the final study follow-up visit/contact will be provided for each treatment group.

3.2.3.5 Seizure Burden Through 72 Hours Following IP Initiation

The seizure burden through 72 hours following IP initiation is described as the percent of time during which there is electrographic seizure activity from IP initiation to 72 hours. Descriptive summary statistics (n, mean, standard deviation, median, 25th and 75th percentiles, minimum, and maximum) of seizure burden will be provided by treatment group. The change from baseline of seizure burden will also be summarized using descriptive statistics by treatment group. The baseline seizure burden is defined for 30 minutes prior to IP initiation.

The number and percentage in each category of seizure burden (<20%, 20-50%, and >50%) will be also summarized by treatment group.

3.2.3.6 Level of Responsiveness as Assessed by the Full Outline of UnResponsiveness (FOUR) Score Scale

The FOUR Score is a tool designed to assess participants with impaired level of consciousness. It has a 17-point scale (with potential scores ranging from 0 to 16). The FOUR Score assesses four domains of neurological function: eye responses, motor responses, brainstem reflexes, and respiration. Each component is a 5-point scale, ranging from 0 to 4.

Descriptive summary statistics (n, mean, standard deviation, median, 25th and 75th percentiles, minimum, and maximum) will be provided by treatment group and by scheduled visit for total FOUR Score.

Count and percentage of each scale for each component will also be provided by treatment group and by visit.

3.2.3.7 Level of Sedation as Assessed by the Richmond Agitation and Sedation Scale (RASS)

The RASS is a medical scale used to measure the agitation or sedation level. It is a 10-point scale, with four levels of anxiety or agitation (+1 [restless] to +4 [combative]), one level to denote a calm and alert state (0), and 5 levels of sedation (-1 [drowsy] to -5 [unarousable]).

Count and percentage of each scale for each component will be provided by treatment group and by visit.

3.2.3.8 Clinician Global Impression-Improvement (CGI-I)

The CGI-S and CGI-I assess overall health and functional status of a participant. Participant and

clinician rater versions indicate general worsening or improvement on a seven-point Likert-like scale.

The CGI-S contains a 7-point Likert scales for baseline overall severity of the participant's presentation (ranging from 1 = normal to 7 = very severe problem) and the CGI-I contains a 7-point Likert scale for overall global impression of change relative to baseline (ranging from 1 = very much improved to 7 = very much worse).

Descriptive summary statistics (n, mean, standard deviation, 25th and 75th percentiles, median, minimum, and maximum) will be provided for CGI-I score by treatment group and by schedule visit. Count and percentage of each scale for CGI-S and CGI-I will be summarized by treatment group and by visit.

3.2.3.9 Level of Functioning as Assessed by the Modified Rankin Scale (mRS)

The Modified Rankin Score (mRS) is a 6-point disability scale with possible scores ranging from 0 (no symptom at all) to 5 (severe disability). A separate category of 6 is usually added for participants who expire.

Descriptive summary statistics (n, mean, standard deviation, 25th and 75th percentiles, median, minimum, and maximum) will be provided for mRS score by treatment group and by schedule visit. Count and percentage of each scale will be summarized by treatment group and by visit.

3.2.3.10 Level of Functioning as Assessed by the EuroQoL (EQ-5D-5L)

The EuroQoL (EQ-5D-5L) is a standardized measure of health-related quality of life which comprises five dimensions: mobility, self-care, usual activities, pain/discomfort, and anxiety/depression. Each dimension has 5 levels: no problems, slight problems, moderate problems, severe problems, and extreme problems.

Descriptive summary statistics (n, mean, standard deviation, 25th and 75th percentiles, median, minimum, and maximum) will be provided for EQ-5D-5L index score by treatment group and by schedule visit. Count and percentage of each level for each dimension will be summarized by treatment group and by visit.

3.2.3.11 Proportion of Participants with mRS ≥ 3 at the Time of Hospital Discharge

Count and percentage of participants with mRS ≥ 3 at the time of hospital discharge will be provided for each treatment group.

3.2.3.12 Proportion of Participants With No Progression to IV Anesthesia for 4 Weeks Following IP Initiation

The number and percentage of participants with no progression to IV anesthesia for 4 weeks

following IP initiation will be summarized by treatment group.

3.2.4 Healthcare Utilization Endpoints

All the healthcare utilization endpoints analysis will be conducted in the ITT population. Healthcare utilization endpoints will be summarized descriptively by treatment group. No formal statistical comparisons are planned for these endpoints.

3.2.4.1 Time on Positive Pressure Ventilation After IP Initiation

Time on positive pressure ventilation will be analyzed by a stratified log-rank test, where the time to event for each participant is defined as time from treatment initiation (or positive pressure ventilation initiation if the participant was not on ventilation at the start of treatment) to positive pressure ventilation being off, whether the participant was on ventilation at the start of treatment is used as the stratification factor. Participants who never needed positive pressure ventilation are defined to have 0 amount of time on positive pressure ventilation. Participants who died before getting off positive pressure ventilation will be censored at the latest possible assessment time. Participants who never got off positive pressure ventilation while on study will be censored at the last assessment time. The quartiles (1st [25% percentile], 2nd [median], 3rd [75% percentile]) and the associated 95% CI will be provided based on the Kaplan-Meier estimate of the survival curves.

3.2.4.2 Proportion of Participants Requiring Positive Pressure Ventilation Initiated During IP Infusion

Proportion of participants requiring positive pressure ventilation initiated during IP infusion will be summarized by count and percentage by treatment group. The summary will be based on participants who were not on positive pressure ventilation at baseline.

3.2.4.3 Length of Stay in ICU and in Hospital

Post IP initiation Length of stay (hours) in ICU = Time of discharge from ICU – IP initiation time

Length of stay (hours) in hospital = Time of discharge from hospital – IP initiation time

Length of stay will be summarized with descriptive statistics (n, mean, standard deviation, median, 25th and 75th percentile, min and max) by treatment group.

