3.1.1 Double-blind Phase

Approximately 160 participants were planned to be screened to randomize approximately 124 study participants at least 12 years of age with SE. Randomization stopped at 100 patients for business reasons. Randomized participants will receive ganaxolone IV solution or placebo, referred to as investigational product (IP), in a 1:1 ratio added to SE standard of care.

[figure not shown]
Potential participants may be identified in the emergency department, ICU or other units in the hospital and will be consented/assented or deferred, where allowed by law and then screened for inclusion/exclusion criteria prior to being randomized to start IP treatment.

Investigational product will be added to standard of care following failure of any two or more antiseizure treatments (benzodiazepine and 1 IV AED or 2 IV AEDs). Investigational product will be administered as a 48-hour continuous infusion, which includes an initial 3-minute bolus and ends with a 12-hour taper.

After the IP has been discontinued (with or without taper), the follow-up period study assessments/procedures will be collected every 24 hours through 120 hours (or until hospital discharge) and at the time of hospital discharge followed by weekly follow-up visits/contacts at Week 1, 2, 3, and 4.

Weeks 1, 2, 3, and 4 visits can be conducted as an inpatient visit for participants who are still in the hospital, or as a telephone contact for participants who have been discharged. Attempts should be made to have discharged participants return for one of these visits to be in person. In total, each participant will be followed for approximately 4 weeks following IP initiation.

Figure 1. Study Design Flow Chart

Treatment is planned to be 2-days (including a 12-hour taper).

Hours 24-36 should start with an infusion rate of 20mg/hr with dose adjustments allowed up to 45mg/hr.
Upon IP discontinuation (with or without taper) participant will continue into the Follow-up Period

Total participation is expected to be approximately 4 weeks.

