6.2.5 Medical Oversight

Participants will require close medical monitoring as defined by local institutional practice guidelines for the treatment of patients with the diagnosis of seizures or status epilepticus.

Telemedicine

Telemedicine is an acceptable practice for conducting protocol-driven assessments/procedures as defined by local institutional practice guidelines.

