7.1.1 Screening Period

7.1.1.1 Screening

Potential participants may be identified in the emergency department, ICU, or other units in the hospital, and will be consented/assented and then screened for inclusion/exclusion criteria prior to being enrolled to start IP treatment.

Procedures specific to this protocol and not otherwise considered standard of care, will not be performed until written informed consent/assent from the participant/participant’s parent/guardian/LAR has been appropriately obtained or deferred, where allowed by law. Consent for participants who are at risk for SE may be obtained prior to occurrence of SE, this is also referred to as pre-consenting. Additional details on consent/assent can be found in [Section 11.3.1](#).

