2.5 Handling of Missing Data

Unless stated otherwise, there will be no imputation of incomplete or missing data other than the dates mentioned below. Missing efficacy data will be imputed in a sensitivity analysis as described in [Section 3.2.1.1](#).

The handling of partial start and stop dates for AEs are described in [Table 2](#) below. Similar algorithms for handling missing and partial dates of concomitant medication usage are described in [Table 3](#). In both cases, if a stop date is complete and an imputed start date is after the stop date, the start date will be set to the stop date.

Table 2: Adverse Event Start/Stop Date Imputation

Parameter	Missing	Additional Conditions	Imputation
Start date for AEs	D	M and Y same as M and Y of initiation of IP infusion	Date of initiation of IP infusion
		Y same but M prior to month of initiation of IP	Last day of month
		Y same but M after month of initiation of IP infusion	First day of month
		Y is prior to year of initiation of IP infusion	Last day of month
		Y is after year of initiation of IP infusion	First day of month
	M	Y is same as Y of initiation of IP infusion	Month of initiation of IP infusion
		Y is prior to year of initiation of IP infusion	M = December
		Y is after Y of initiation of IP infusion	M = January
	D and M	Y same as Y of initiation of IP infusion	Date of initiation of IP infusion
		Y prior to Y of initiation of IP infusion	M and D will be December 31
		Y after Y of initiation of IP infusion	M and D will be January 1
	Y, or M, D, Y	Y and/or start date missing	Date of initiation of IP infusion
Stop date for AEs	D	M and Y not missing	Use last day of month (i.e., D may take on values of 28, 29, 30, or 31, depending on month)
		Y not missing; if D also missing, impute D as described above	M = December
	Y, or M, D, Y	Y and/or stop date missing.	No imputation. Date left missing.

D=day, M=month, Y=year

Note: In all cases, if an estimated start date is after a complete stop date, the start date will be set to the AE stop date. Similarly, if the estimated stop date is before a complete or imputed start date, use the last day of the start day month.

Table 3: Imputation for Prior/Concomitant Medication Missing and Partial Dates

Parameter	Missing	Additional Conditions	Imputation
Start date for con meds	D only	M and Y are not missing or imputed.	Use 1 st day of M.
	M only	D and Y are not missing or imputed.	M = January
	M and D	Y is not missing or imputed.	Use Jan 01 of Y

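### ICU length of stay is counted from IP initiation rather than ICU admission, so later entrants gain hours they did not spend there and participants never in the ICU have no value

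*SAP*

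**What the plan says.** SAP 3.2.4.3 gives the whole derivation in one line: "Post IP initiation Length of stay (hours) in ICU = Time of discharge from ICU" minus the IP initiation time. The ICU admission time does not enter it. The section then states: "Length of stay will be summarized with descriptive statistics (n, mean, standard deviation, median, 25th and 75th percentile, min and max) by treatment group". It has no rule for a participant never in the ICU, one who enters later, or one readmitted. It also has none for a participant who dies or is still there at last contact.

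SAP 3.2.4 places the endpoint in the ITT population, which is not restricted to ICU patients, and plans no formal comparison. SAP 2.5 says that, unless stated otherwise, "there will be no imputation of incomplete or missing data other than the dates mentioned below". Protocol 10.4.4 names the endpoint without defining it further.

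On location, Protocol 3.1.1 says "Potential participants may be identified in the emergency department, ICU or other units in the hospital", and Protocol 7.1.1.1 repeats this. On level of care, Protocol 6.2.5 says "Participants will require close medical monitoring as defined by local institutional practice guidelines". Neither section makes ICU care a condition of treatment.

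The section just before, SAP 3.2.4.1 on ventilation, handles the same structure differently. Its clock starts at ventilation initiation if that comes after treatment start, and "Participants who never needed positive pressure ventilation are defined to have 0 amount of time on positive pressure ventilation".

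**The concern.** A duration needs both a start and an end. The SAP takes the end from the ICU and the start from the infusion, and the two match only if the participant is in the ICU when the infusion begins. Otherwise the formula counts time spent elsewhere as ICU time, or returns nothing.

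The missing values matter more than the extra hours. Whether a participant ever enters the ICU may be settled after randomisation, and treatment may influence it. A summary limited to those admitted therefore compares subsets that need not be alike. A difference between arms in how often the ICU is used, in either direction, would not show in the mean or median. Healthcare resource utilisation is an exploratory objective of the trial, and ICU stay is one of the few endpoints that serve it.

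**Working it through.** The documents give no ICU figures, so there is no plan figure to reproduce. The check applies the formula to simple histories and compares the result with time actually spent in the ICU after IP start.

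**Formulas**, with IP initiation at hour 0:

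- SAP value = ICU discharge time − 0.
- Actual value = sum over ICU stays of max(0, ICU discharge − the later of ICU admission and 0), and 0 h if never admitted.
- For one stay entered at hour d after IP start, SAP − actual = discharge − (discharge − d) = d.

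**Single participants** (hypothetical):

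| ICU history | SAP value | Actual ICU hours |
|---|---|---|
| In the ICU at hour 0, out at 96 | 96 | 96 − 0 = 96 |
| Enters at 24, out at 96 | 96 | 96 − 24 = 72 |
| Enters at 48, out at 72 | 72 | 72 − 48 = 24 |
| Left the ICU 10 h before IP start, no return | −10 | 0 |
| Never in the ICU | none | 0 |

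With a readmission, the SAP does not say which discharge counts. The first ignores the second stay; the last includes ward time between the stays.

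**Never admitted, at arm level.** Assume a share q of the arm never enters and everyone else stays 96 h from IP start. The SAP mean is 96 h for any q. The mean with zeros is 96 × (1 − q):

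- q = 10%: 96 × 0.9 = 86.4 h
- q = 20%: 96 × 0.8 = 76.8 h
- q = 30%: 96 × 0.7 = 67.2 h
- q = 40%: 96 × 0.6 = 57.6 h

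With 100 randomised 1:1, or about 50 per arm, the reported n would fall to 50 × 0.9 = 45 at the low end and 50 × 0.6 = 30 at the high end.

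Under the same assumption, the between-arm difference left out is 96 h times the difference in never-admitted shares. That is 96 × 0.01 = 0.96 h per percentage point, whichever arm has the larger share, and nothing if the shares are equal.

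**Late entry, at arm level.** Assume a share r of ICU users enters d hours late. The mean is too high by r × d: from 0.1 × 6 = 0.6 h to 0.3 × 48 = 14.4 h.

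The values of q, r, d and 96 h are all assumptions.

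**The case against.** The strongest case against is that the affected group may be small. Inclusion criterion 3b selects patients for whom IV anesthesia is the likely next step. Exclusion 4 removes those who could not receive it. Treatment is a 48-hour infusion with continuous EEG. Many participants may already be in the ICU at IP start, where the formula is correct for a single stay. This stands as a limit on size. It does not repair the definition, because neither document requires ICU care.

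Second, the protocol says where participants may be identified, not where the infusion starts. A reader might infer that IP is documented as starting in the emergency department or on a ward. It is not; the text leaves that possible and no more.

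Third, n is reported by arm, so a shortfall would be visible. That is true, but n alone does not separate never admitted from missing, died or still in the ICU. Hospital length of stay, reported alongside, does not depend on ICU entry, but it does not measure ICU use.

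Fourth, SAP section 5 leaves detail to programming specifications that are not shown. These might settle readmissions and never-admitted participants. They would have to depart from the stated formula to correct late entry.

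Finally, scoring every participant never in the ICU as 0 h would give a death outside the ICU the best possible value. The protocol synopsis cites 16 to 39% mortality in refractory SE, so this objection stands and shapes the fix.

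**Conclusion.** The definition should be corrected. As written, it overstates ICU time by exactly the delay to ICU entry and gives no value to participants never admitted. No other section supplies the missing rules, although SAP 3.2.4.1 has both for ventilation. The size is unknown. The ranges in the working show what the rule does under assumed shares and stays; they do not estimate what will happen in this trial.

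A reader might infer that the formula hides a benefit of ganaxolone, or removes participants mainly from the better arm. The documents do not support that. It presumes a treatment effect on ICU entry, for which they give no figures, and the loss could fall equally on both arms or run the other way. What can be said is that the summary is conditional on a post-randomisation event.

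The endpoint is descriptive and outside the testing hierarchy. Type I error, power and the co-primary conclusions are untouched, so this is a minor correction.

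**What to change.** Redefine ICU length of stay in SAP 3.2.4.3 as total ICU hours after IP initiation: the sum, over ICU stays ending after IP initiation, of ICU discharge minus the later of ICU admission and IP initiation. Assign 0 h to participants never in the ICU after IP initiation who were discharged alive. This brings the section into line with the later-start and zero rules of SAP 3.2.4.1.

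Report by arm the number never admitted, the number who died (not scored as 0 h) and the number still in the ICU at last contact.

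The text change is a few sentences. The distribution will be skewed with a cluster at zero, so the median and quartiles already planned should carry the summary. The fix also needs ICU admission times for every stay. Protocol 7.3 says when the Hospitalization Questionnaire is collected but not what it records. If it lacks admission times, they must be retrieved from hospital records, retrospectively for participants already treated, since enrollment has stopped.

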3.2.4.4 Discharge Destination

Discharge destination is the location where the participant is living at the last follow-up assessment.

Count and percentage of each discharge destination will be summarized by treatment group.

3.2.5 Open-label Phase Efficacy Summary

Efficacy assessments for the open-label phase will be summarized using descriptive statistics.

3.3 Safety Analysis

All the safety summaries are based on the Safety Population. Baseline is defined as the last non-missing value prior to the first dose of study drug administration.

3.3.1 Adverse Events

Adverse events (AEs) will be coded by MedDRA® version 22.0 or higher and grouped by SOC and PT. The verbatim term will be included in the AE listings. Except where indicated, the summary tables will include only TEAEs. All AEs, treatment-emergent or otherwise, will be presented in participant data listings.

A treatment-emergent adverse event (TEAE) is defined as an AE that occurred or worsened at the time of or following IP initiation. To allow differentiation between the study period in which an AE occurred, two categories are defined based upon onset date. Adverse events that had onset dates prior to the IP initiation are considered "prior." Adverse events with onset dates on or after IP initiation and up to the end of the follow-up period are considered "on-therapy" or equivalently "treatment emergent". Adverse events with onset dates prior to the IP initiation but that worsen after IP starts will be considered treatment emergent.

An overview table, including number and percentage of participants with AEs, TEAEs, TEAEs by highest severity, serious TEAEs, study drug related TEAEs, TEAEs leading to IP discontinuation, and TEAEs leading to death will be provided.

In addition, the following summary tables will be provided:

- TEAE by SOC and PT
- TEAEs by PT
- TEAE by SOC, PT, and severity
- Study drug related TEAE by SOC and PT
- Serious TEAE by SOC and PT
- Serious and drug-related TEAE by SOC and PT
- TEAEs leading to study drug discontinuation by SOC and PT
- TEAEs leading to withdrawal

All AE tables will be sorted by SOC and PT in decreasing frequency of the number of participants in the GNX-treated group. If frequency ties, the sorting will be alphabetic.

A participant having the same AE more than once will be counted only once in the number and percentage of participants' calculation for that AE. Similarly, if a participant had more than one AE in a SOC, the participant will be counted only once in the number of participants with an AE for that SOC. If a participant has the same AE on multiple occasions, the highest severity (severe > moderate > mild) recorded for the event will be presented in the AEs by severity table.

Adverse event listing will be provided for all TEAE, serious TEAEs, TEAE related to IP, TEAE leading to study drug discontinuation, AEs leading to withdrawal, and participants who died during the study.

